Mycophenolate mofetile	1000 mg BID start on day one post-transplant	1000 mg BID start on day one post-transplant
Corticosteroids	As per Transplant Center Immunosuppression Protocol - Taper off between 21 days-6 months post LT	As per Transplant Center Immunosuppression Protocol - Taper off between 21 days-6 months post LT

The Data Safety Monitoring Board (DSMB) will review the data on the first 30 subjects who have completed 30 days study enrollment.

Primary Endpoints:

- The incidence of AKI at 30 days post-transplant.
- Serum creatinine and eGFR at 30 days post-transplant.

Secondary Endpoints:

- The incidences of acute cellular rejection, (ACR), at 30 days post-transplant.
- Patient survival at 6 months post-transplant.
- Graft survival at 6 months post-transplant.
- The incidences of AEs and SAEs.

The primary endpoint for the study is a composite renal endpoint of Acute Kidney Injury, (**stages 2 to 3**), at 30 days post OLT. The staging of AKI will follow the classification system proposed by the Acute Kidney Injury Network (AKIN) depicted in **Table 2**.²⁶

TABLE 2: Classification / Staging for Acute Kidney Injury (AKI)

Classification/Staging System for Acute Kidney Injury ²⁶		
Stage:	Serum Creatinine Criteria	Urine Output Criteria:
1	Increase in serum creatinine of ≥ 0.3 mg/dL, (≥ 26.4 $\mu\text{mol/L}$), or an increase of $\geq 150\%$ to 200% , (1.5 to 2-fold), from baseline.	Less than 0.5 mL/kg per hour for more than 6 hours
2	Increase in serum creatinine of $> 200\%$ to 300% , (>2 to 3-fold), from baseline.	Less than 0.5 mL/kg per hour for more than 12 hours
3 ^a	Increase in serum creatinine to more than 300% , (>3 -fold), from baseline, (or serum creatinine of ≥ 4 mg/dL, [≥ 354 μmol], with an acute increase of ≥ 0.5 mg/dL, [44 $\mu\text{mol/L}$].	Less than 0.3 mL/kg per hour for 24 hours, or anuria for 12 hours.

^aOnly **one criterion** (creatinine or urine output) must be fulfilled to qualify for a stage. Individuals receiving renal replacement therapy (RRT) are considered to have met the criteria for **Stage 3** irrespective of the stage they were in at the time of RRT.

B. Patient Population

Study participants will be recruited from the Liver Transplant Programs at Cleveland Clinic, Cleveland, Ohio; University of Cincinnati, Cincinnati, Ohio; Medical College of Wisconsin Milwaukee, Wisconsin, and Cleveland Clinic Weston, Florida

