C. Number of Patients: One hundred and ten (110) liver transplant recipients will be enrolled in this study, **approximately** 40-50 patients at Cleveland Clinic, (the lead center), and 15-25 patients at each of the three additional participating centers (number of enrollment may vary at different centers).

Sample size estimates for study of liver dysfunction

Sample sizes were computed on the bases of using Welch’s two-sample t-tests to compare changes in creatinine between the control and the thymo 4.5 groups. Assumptions regarding differences in means and standard deviations for each group were based on the results of preliminary data and are given in Table 3. The smaller of the two standard deviations was varied along a range from that observed in the preliminary data to being equal to the larger standard deviation. The former would tend to yield smaller sample sizes, while the latter larger. Assuming that 10% of the patients that are initially enrolled will drop-out before 12 months values are measured, the sample sizes indicated should be increased by 10% to account for this drop-out.

These calculations were done using SAS software (version 9.3, Cary, NC). A significance level of 5% and two-tailed tests were assumed for all testing.

For delta creatinine, we are assuming a difference in means between groups of 0.32. In the pilot data delta creatinine in the control group had a standard deviation of 0.51, while the thymo 4.5 group a standard deviation of 0.12. Therefore, three levels of standard deviation—0.12, 0.32, and 0.51. Based on these calculations, enrolling enough patients to meet the sample size requirements for detecting differences in delta creatinine (within 2 SD, 0.32) will mean having ample sample size for detecting differences in month 12 GFR. Accordingly, we noticed that a sample size of 110 (55 in each group) would give us 90% power with the safest margin for 10% dropouts throughout the study.

Table 3. Minimum sample sizes need to achieve desired levels of power

Comparison	Difference	SD1	SD2	Power	
				80%	90%
Delta Creatinine	0.32	0.51	0.12	46	60
			0.32	58	78
			0.51	82	110
Month 12 GFR	36.8	26.6	20.5	16	20
			23	18	22
			26.6	20	26

D. Selection of Study Population:

INCLUSION CRITERIA

- Patients undergoing deceased donor solitary liver transplantation.
- Age 18 – 75 years at the time of transplantation.
- Willingness and ability to comply with the study procedures.
- Signed Informed Consent Form.

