A randomization schedule will be generated and kept by each transplant center, after approval of the protocol by the Cleveland Clinic IRB, and each participating center's respective IRB, and prior to Study Start-up. Randomization numbers will be assigned in the order in which subjects qualify for treatment, not in the order of study subject enrollment.

Subject randomization will be performed provided the patient has signed the Informed Consent AND met all Study Entry Criteria, (Inclusion and Exclusion), **AND is "Enrolled" into the Study. Randomization will be performed within 6 hours of the patient's arrival to the Intensive Care Unit, (ICU),** after the transplant procedure. Subjects will be randomized in a 1:1 fashion to receive delayed CNI with 4.5 mg/Kg Thymoglobulin® [Group 1], or early CNI therapy [Group 2]. All subjects will receive maintenance therapy with MMF and corticosteroids.

G. Early Patient Withdrawal/Study Treatment Discontinuation

Subjects may voluntarily withdraw from the study or be withdrawn from the study, at the discretion of the investigator, at any time. A patient should be withdrawn from the study if the investigator believes that continuation would be detrimental to the patient's well-being. Reasons for **Study Treatment Discontinuation / Early Patient Withdrawal** are:

- Death after consent, but prior to randomization.
- Graft loss and/or re-transplantation.
- Pregnancy.
- Withdrawal of informed consent, (subject's decision to withdraw for any reason).

- Any clinically significant AE/SAE(s), laboratory abnormality, and/or incurrent illness which, in the opinion of the investigator, indicates that continued treatment with study therapy and/or further participation in the study, (including obtaining vital status of the subject and allograft), is not in the best interest of the subject.
- Unsatisfactory therapeutic effect (e.g. repeated acute rejection).
- Termination of the study by the investigating center or withdrawal of funds by Sanofi.
- Significant protocol violation.
- Protocol deviation resulting in significant patient safety risk.
- Subjects who for any reason cannot be followed and/or are unable to meet the requirements of the protocol.

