Designated Study Personnel, (at each Study Site), must enter the information required by the protocol onto the paper Case Report Forms (CRFs). The information from the paper CRFs will then be entered directly into the electronic Database, REDCAP, by designated Study personnel at each Study Site. Edit checks and double data entry with verification upon second entry are built

into specific data items. Text items (e.g. comments) are entered once. Queries are sent to the investigational site using an electronic data query. Designated investigational Study Site staff will be required to respond to all queries and make any necessary changes to the data. Other errors or omissions are entered on Data Query Forms, which are made accessible to the investigational site for resolution.

Concomitant medications entered into the database will be coded using the WHO Drug Reference List which employs the Anatomical Therapeutic Chemical classification system. Coexistent diseases and Adverse Events (AEs) will be coded using the Medical dictionary for regulatory activities (MedDRA) terminology.

D. Handling of Missing Values/Censoring/Discontinuations

Since the study subjects will be followed for renal function, graft loss, or survival status, the subjects with missing measurements at 30 days will only be those who die, withdraw consent or are lost to follow-up. It is expected there will be very few such patients within 30 days. Missing values at day 30 will be imputed using the last observation carried forward (LOCF) approach. Missing baseline serum creatinine values will be replaced with the most recent available value from the pre-transplant period.

STUDY ENDPOINTS / EFFICACY AND SAFETY

A. Primary Endpoints:

Efficacy and Safety (Primary):

Primary Efficacy and Safety variables to be evaluated at 30 Days Post Liver Transplant are:

- Incidence of AKI
- Serum creatinine and eGFR

B. Secondary Endpoints:

Efficacy and Safety (Secondary):

Secondary Efficacy and Safety variables to be evaluated at 30 Days Post Liver Transplant are:

- The incidences of acute cellular rejection, (ACR), at 30 days post-transplant.
- Patient survival at 6 months post-transplant.
- Graft survival at 6 months post-transplant.
- Incidence of AEs / SAEs

C. Additional Efficacy and Safety Variables for Evaluation:

- Patient survival at 12 months post-transplant
- Graft survival at 12 months post-transplant

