- Biopsy-proven acute allograft rejection rates at 6 Months and 12 Months post-transplant.
- AKI (Stage 3 rates) at 3 Months post-transplant
- Renal function measured by eGFR at 12 Months post-transplant
- Microbiologically-proven systemic infection rates at 6 Months and 12 Months post-transplant
- Hepatitis C viral loads (in HCV positive recipients) at 12 Months post-transplant
- Incidence of biopsy proven recurrence of HCV infection at 12 Months post-transplant
- Incidence of AEs and SAEs at 12 months post-transplant

For each efficacy event, simple event rate estimates (proportion of events) at 12 months will be obtained, and event rates between the two treatment groups will be compared using Z-statistic based, two-sided, 95% confidence interval for RC – RE, where RC and RE are the event rates for the Early CNI treated Control Group and the Late CNI Initiated/Thymoglobulin® Study Group, respectively. In addition, for the composite efficacy endpoint and its components, individually, Kaplan-Meier survival methods will be used to estimate probabilities of efficacy events by visit. Greenwood’s formula will be used to estimate standard errors and to derive the two-sided, 95% confidence interval of RC – RE, by visit window. HCV replication in HCV positive patients will be compared with summary statistics.

Due to the short duration of study involvement, we expect very few patients to be lost to follow-up, or to withdraw consent. Therefore, for the composite efficacy endpoint, patients who are discontinued from the study for these two reasons, (prior to the incidence of death, graft loss, or biopsy-proven acute cellular rejection), will not be considered as efficacy failures. If there are an adequate number of subjects from each clinical center, a formal test of center by treatment interaction effect will be made.

Adverse Events (AEs) / Infections:

Generally, infections are analyzed together with Adverse Event data. **In addition, infections will be analyzed separately. Infections will be documented on both, the Infection CRF and the AE CRF.** The data collected on both CRFs will be coded with the MedDRA dictionary which gives preferred term and body system information.

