Adverse Event and Infection data are to be analyzed as a whole under the heading of “Adverse Events” for each treatment group. The incidence of Adverse Events will be summarized by body system, severity, and causal relationship to Study Drug. All information pertaining to Adverse Events, noted during the study, will be listed by patient. Verbatim details, provided by the Study Site Investigator, are to include:

- **The preferred term**
- **The body system**
- **Start Dates / End Dates**
- **Severity**
- **Relationship to Study Drug**

The “onset” of the Adverse Event” will also be shown, (relative in number of days), to the day of Initial Dose of Study Drug, for those subjects randomized to **Group 1/Arm 1** of the Study. Infection data will be further coded with SNOMED for micro-organism cultured and type of infection, (viral, bacterial, fungal, etc.). The incidence rate of infection (**by type and micro-organism**) will also be tabulated for each treatment group.

Laboratory Data:

Abnormal laboratory values, according to notable criteria, will be identified. A by-patient listing of laboratory data, for patient/lab abnormalities, will be generated. Laboratory values, outside the clinically notable and expanded limits, will be flagged. Appropriate incidence rates of clinically notable abnormalities will be provided by treatment. Further, for each laboratory parameter, a table summarizing the by visit laboratory values, (MDRD eGFR and serum creatinine), will be provided.

REFERENCES:

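### Day-30 serum creatinine and eGFR are listed as primary but no analysis is named for them; ANCOVA on baseline and centre would settle value versus change at small cost

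*Combined protocol and SAP*

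**What the plan says.** The synopsis, the Overall Study Design section and the Study Endpoints section all list "Serum creatinine and eGFR at 30 days post-transplant" as primary, beside AKI. Overall Study Design then adds: "The primary endpoint for the study is a composite renal endpoint of Acute Kidney Injury", restricted to stages 2 to 3.

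Four places come near an analysis of creatinine or eGFR:

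- **Number of Patients (sample size).** The size rests on Welch's "two-sample t-tests to compare changes in creatinine between the control and the thymo 4.5 groups". No time point is given for the creatinine change. The second quantity in Table 3 is Month 12 GFR, and the 10% dropout is counted to 12 months.
- **Additional Efficacy and Safety Variables.** The named method is for events: "event rates between the two treatment groups will be compared using Z-statistic based, two-sided, 95% confidence interval". Kaplan-Meier estimates are added for the composite. Centre appears only here: if numbers allow, "a formal test of center by treatment interaction effect will be made".
- **Handling of Missing Values.** Missing day-30 values are imputed by LOCF. For baseline, "Missing baseline serum creatinine values will be replaced with the most recent available value from the pre-transplant period".
- **Laboratory Data.** The plan promises that "a table summarizing the by visit laboratory values, (MDRD eGFR and serum creatinine), will be provided".

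On randomisation, Treatment Group Assignment says "A randomization schedule will be generated and kept by each transplant center". It mentions no blocking.

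**The concern.** None of these texts says how the arms will be compared on day-30 creatinine or eGFR. The endpoint is worded as a level, creatinine is sized as a change, and GFR is sized with no change stated. Three analyses are therefore open: the value, the change, or the value adjusted for baseline. Change scores and the AKI creatinine criteria use baseline, but no comparison uses it as a covariate. Centre is not in any main comparison although each centre has its own randomisation schedule.

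An unadjusted comparison is valid under randomisation. What is at stake is an unfixed choice in an open-label trial, and precision left unused. Value and change can differ widely in standard error, and picking the better of the two after seeing the data inflates the type I error.

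**Working it through.** **1. The plan's own figure.** Inputs from Number of Patients: difference 0.32, SD 0.51 in the control arm and 0.12, 0.32 or 0.51 in the other, two-sided 5%, Welch test. Power from the noncentral t with Satterthwaite df gives total N for 80%/90% power of 46/60, 58/78 and 82/110, exactly as in Table 3. At 55 per arm with both SDs 0.51, SE = 0.51 × √(2/55) = 0.0973, 0.32/0.0973 = 3.29, and power is 90.3%. With the second SD at 0.32 or 0.12 it is 97.4% or 99.4%.

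These powers apply at day 30 only if 0.32 and the SDs are day-30 figures, which the section does not say. The GFR difference is a 12-month figure: 36.8 = 87.8 − 51.0, the highest and lowest one-year pilot eGFR values quoted under Overview of Thymoglobulin Safety.

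**2. Value, change and ANCOVA.** Let ρ be the correlation of baseline with day 30, and k the baseline SD divided by the follow-up SD. The documents give neither, so both are assumed. Variance ratios:

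- change / value = 1 + k² − 2ρk
- ANCOVA / value = 1 − ρ²
- ANCOVA / change = (1 − ρ²) / (1 + k² − 2ρk)

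For example, at ρ = 0.7 and k = 1: change/value = 2 − 1.4 = 0.6 and √0.6 = 0.775, so the SE is 23% smaller.

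| Difference in SE | ρ = 0.3 | 0.5 | 0.7 | 0.9 |
|---|---|---|---|---|
| Change vs value, k = 1 | +18% | 0 | −23% | −55% |
| ANCOVA vs value | −5% | −13% | −29% | −56% |
| ANCOVA vs change, k = 1 | −19% | −13% | −8% | −2.5% |
| ANCOVA vs change, k = 0.5 | −2% | 0 | −4% | −26% |

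**3. The same in power.** Hold the SD of change at 0.51 in both arms, k = 1, difference 0.32, 55 per arm. The SD of the value is 0.51/√(2(1 − ρ)) = 0.431, 0.510, 0.658 and 1.140. Welch on the value then has power 97.1%, 90.3%, 71.4% and 30.8%, against 90.3% for change. ANCOVA with ordinary standard errors has residual variance 0.51² × (1 + ρ)/2. With df = 110 − 2 − 4 = 104 and variance inflation 1 + 4/103, its power is 97.8%, 95.9%, 93.4% and 90.7%.

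**4. Cost of leaving the choice open.** In simulation under no effect (8,000 trials at each of ρ = 0.3, 0.5, 0.7), taking the better of value and change rejected 8.9% to 9.6% of the time, against a nominal 5%. With baseline in the model, value and change give the same treatment estimate and standard error (check dataset: 0.3962, SE 0.0698 both ways).

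**5. Net of a robust standard error.** The pilot SDs of change, 0.51 and 0.12, are very unequal, so HC3 was used. Simulation: N = 110, centres 44/22/22/22 (assumed, within the planned ranges), no centre effect, model with treatment, baseline and three centre terms, mean HC3 SE against Welch's. The first four rows use 1:1 balance within centre.

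| Scenario | Mean SE against Welch |
|---|---|
| vs value, ρ = 0.3/0.5/0.7/0.9 | −1.5/−11/−26/−55% |
| vs change, k = 1, same ρ | −17/−10/−5/+1% |
| vs change, k = 0.5, same ρ | +1/+3/0/−24% |
| vs change, pilot SDs, change/baseline correlation 0/−0.3/−0.5/−0.7 | +3/0/−6/−17% |
| Covariates explain nothing, balance within centre | +3.3 to +3.4% (95th percentile +6.6 to +7.2%) |
| Covariates explain nothing, simple randomisation within centre | +4.8% (95th percentile +10.9 to +12.4%) |

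With pilot SDs and baseline SD 0.3–0.8, the result against raw values runs from 0.2% wider to 57% narrower. Simple randomisation makes the informative cells about 1–2 points less favourable. Coverage of the 95% interval was 94.9–96.4% throughout.

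**The case against.** For creatinine, the sample-size text does name a test, a scale and a significance level, so a natural reading is that change is the intended comparison. Against change, the net gain is modest in many cells, and in some the HC3 interval is up to about 3% wider. The large gains arise mostly against raw values. HC3 also causes most of the cost: with HC2 or ordinary standard errors and useless covariates, the mean SE is only about 0.5% above Welch's under balance and 1.9–2.4% under simple randomisation. HC3 lowers power at 0.32 with both SDs 0.51 by 1.4 to 2.0 points. The simulation has no centre effect, so it cannot show a benefit from centre.

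Much of this is right in its detail, but it does not close the gap. The sizing text is undated, is never carried into the endpoint section and says nothing about how day-30 eGFR is compared. The cheaper HC2 had a type I error of 5.2–5.3% at SDs 0.51/0.12, against 4.6% for HC3, so HC3 is the slightly conservative choice with a known price. Log scale, creatinine in patients on renal replacement at day 30, LOCF after death and the sharing of alpha among the primaries are separate questions that ANCOVA does not answer.

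**Conclusion.** The concern holds. Two listed primary measures have no stated analysis, and the choice between value and change can move the standard error from 18% wider to 55% narrower over the assumed correlations. ANCOVA removes that choice, and with 1:1 allocation is asymptotically at least as precise as both.

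The actual gain cannot be computed from the documents. Introduction section B calls creatinine a strong predictor of renal function after transplant, but also a late and imprecise measure of falling GFR, so a low ρ is possible. The cost if the covariates explain nothing is an HC3 standard error 3.3–4.8% wider on average. The point should be settled before analysis; it does not make an unadjusted comparison invalid, and it does not extend to the AKI analysis.

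**What to change.** State ANCOVA of the day-30 value on treatment, baseline value and centre as the analysis of serum creatinine and, separately, of eGFR, with HC3 standard errors. Keep the unadjusted comparison as a sensitivity analysis and N at 110.

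Calculate baseline eGFR by MDRD from the pre-transplant creatinine. This also reconciles Renal function, which lists eGFR at baseline, with Laboratory Evaluations and Appendix A footnote M, which start it at Day 10.

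The change is wording only. Pre-transplant creatinine and demographics are already collected, so no new data are needed. The model spends four degrees of freedom, one for baseline and three for centre.

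### The planned 110 is the no-dropout 90% figure for both SDs at 0.51; on that row there is no 10% dropout margin and power in 12-month completers is about 87%, and the plan does not name the SD row it relies on

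*Combined protocol and SAP*

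**What the plan says.** All the statements are in *C. Number of Patients*, under the sample size estimates, unless noted.

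- Method: "Sample sizes were computed on the bases of using Welch’s two-sample t-tests to compare changes in creatinine between the control and the thymo 4.5 groups". Also: "A significance level of 5% and two-tailed tests were assumed for all testing".
- Effect: "For delta creatinine, we are assuming a difference in means between groups of 0.32". The control SD is 0.51. The SD in the Thymoglobulin arm (SD2) is set at 0.12 (the pilot value), 0.32 or 0.51.
- Table 3 of that section, total N for delta creatinine at 80% / 90% power: 46 / 60 (SD2 = 0.12), 58 / 78 (SD2 = 0.32), 82 / 110 (SD2 = 0.51).
- Dropout: the section assumes that "10% of the patients that are initially enrolled will drop-out before 12 months values are measured", and therefore "the sample sizes indicated should be increased by 10% to account for this drop-out".
- Conclusion: "a sample size of 110 (55 in each group) would give us 90% power with the safest margin for 10% dropouts".
- The only possible pointer to an SD row is the remark that a size for "detecting differences in delta creatinine (within 2 SD, 0.32) will mean having ample sample size" for month-12 GFR.

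For day 30, *D. Handling of Missing Values/Censoring/Discontinuations* says of patients without a measurement: "It is expected there will be very few such patients within 30 days". Such values are imputed by last observation carried forward.

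**The concern.** The section sets a rule (tabulated size plus 10%) and then reports a final size that is itself a tabulated size. If 110 comes from the row with both SDs at 0.51, the 10% was never added and the stated margin does not exist. If it comes from a row with a smaller SD2, the margin is real and large, but 110 is not the number that row yields. The remark containing 0.32 does not settle this, because 0.32 is both the assumed difference and the middle SD2.

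This sentence is the plan's only justification for enrolling 110. A reader cannot tell whether 110 is the conservative size with no dropout allowance or a mid-range size with a generous one. Many will take it to promise 90% power after 10% loss even in the conservative scenario that the table includes. Lost patients cannot restore the margin, since *G. Early Patient Withdrawal/Study Treatment Discontinuation* rules out replacement.

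**Working it through.** **Inputs** (all from *C. Number of Patients*): Welch t-test, two-sided 5%; difference d = 0.32; SD1 = 0.51; SD2 = 0.12, 0.32 or 0.51; 1:1 allocation; 10% dropout before month 12.

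**Formulas.** SE = √(SD1²/n1 + SD2²/n2); non-centrality = d/SE; Satterthwaite degrees of freedom; power = P(|T| > t₀.₉₇₅,df) for the non-central t.

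**Step 1: reproduce the plan's table.** The smallest equal arms reaching 80% / 90% with no dropout give total N of:

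- delta creatinine: 46/60, 58/78, 82/110;
- month-12 GFR (difference 36.8, SD1 = 26.6): 16/20, 18/22, 20/26.

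All 12 cells agree with Table 3, so the table contains no dropout allowance.

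**Step 2: apply the plan's own 10% rule to the 90% column.**

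| SD2 | Table 3 | × 1.1 | ÷ 0.9 |
|---|---|---|---|
| 0.12 | 60 | 66 | 66.7 |
| 0.32 | 78 | 85.8 (86) | 86.7 |
| 0.51 | 110 | 121 | 122.2 |

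No inflated value is 110. The only match is the uninflated cell for SD2 = 0.51.

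**Step 3: power on the SD2 = 0.51 row.**

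- 55/55: SE = √(0.51²/55 + 0.51²/55) = 0.0973; non-centrality 0.32/0.0973 = 3.29; df = 108; power 90.3%.
- 54/55 (one loss): 90.1%.
- 54/54 (two losses): 89.8%.
- 10% loss: 110 × 0.9 = 99, split 50/49; SE = 0.1025; non-centrality 3.12; df = 97; power 87.1%.

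Against a strict 90% cut this row tolerates one loss; the dropout assumption implies 11.

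**Step 4: the other rows with 99 completers** (50 control, 49 Thymoglobulin).

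- SD2 = 0.32: 95.9%.
- SD2 = 0.12: 98.9%.
- SD2 at which power is exactly 90%: about 0.46.

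**Step 5: what the plan's rule gives on the 0.51 row.** 121 enrolled × 0.9 = 108.9, about 109 completers (55/54); power 90.1%.

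**The case against.** The strongest reply is that the sentence may be correct. If the remark containing 0.32 means SD2 = 0.32, the required 78 becomes 86, and 110 covers that with 95.9% power after 10% loss. Choosing the largest tabulated size so that it absorbs dropout under the smaller SDs would be one way to read a safest margin. Both SDs at 0.51 is also the top of the plan's range, and the pilot SD in the Thymoglobulin arm was 0.12. This much stands: the sentence is false on one row and true on two. But the middle-row reading does not explain why the number is 110, and the text never says that this reading was intended.

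A second reply is that the 87% belongs to no named endpoint. The creatinine endpoint is at day 30, and the renal variable listed for month 12 is eGFR, for which Table 3 needs at most 26 patients. This stands as a limit on the consequence. It does not remove the inconsistency, because the plan itself applies a month-12 dropout rate to the creatinine sizes and then claims a margin for it.

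A third reply is that the one-loss tolerance is too fine: 89.8% after two losses still rounds to 90%. That is fair, since the decline is gradual. Rounding does not bring 87.1% back to 90%.

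**Conclusion.** The concern holds. On the only row that yields 110 (both SDs 0.51), 90% power is a no-dropout figure. With the plan's own 10% loss before month 12 it falls to about 87%, a shortfall of about 3 percentage points. With SD2 at 0.32 or 0.12, 110 covers 10% dropout comfortably, and 90% holds up to an SD2 of about 0.46. The defect is therefore a margin that does not exist on one row, together with an unnamed row and an unstated time point for delta creatinine. It does not show that the trial is underpowered.

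The figures assume the plan's difference of 0.32, a control SD of 0.51, a two-sided 5% Welch test and losses spread almost evenly over the arms. They describe 12-month completers. They should not be read onto the day-30 endpoints, where few values are expected to be missing and those are imputed. The correction should be made, but it is modest in size.

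**What to change.** Name the SD2 row and the time point of delta creatinine behind 110. Remove the claim of a margin for 10% dropout and replace the sentence with:

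> 110 enrolled gives 90% power for a 0.32 difference with both SDs 0.51 and no dropout; with 10% dropout before month 12 (about 99 evaluable), power is about 87% if SD2 = 0.51, about 96% if SD2 = 0.32 and about 99% if SD2 = 0.12.

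This wording is true whichever row the sponsor had in mind. The 87% should not be attached to the day-30 endpoints.

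The cost is one sentence plus the row and time point. Enrolment, analysis and conduct are unchanged, and the stated power drops by about 3 points on the SD2 = 0.51 row only.
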